Refractory, pharmaco-resistant patients are a challenge for multiple medical departments, and it becomes necessary to consider alternative strategies (Leadley et al., 2012). To do so, we propose a shift from a disease-oriented to a mechanism-based management strategy of chronic pain. Chronic pain is a complex sensory and emotional experience that varies widely among people, depending on the context, individual construct of pain, and physiological state (Bushnell et al., 2013). It is defined as a persistent (lasting beyond 3 months) and maladaptive response, without the protective function of acute nociceptive pain (Treede et al., 2015; Merskey & Bogduk, 2012).

Although chronic pain diseases are very heterogeneous in terms of aetiology and clinical manifestations, they may share similar pathophysiological mechanisms related to the processing and inhibition of pain. Thus, multiple studies confirm that chronic pain sufferers tend to present a pattern of increased excitability to pain, and limited central analgesic regulation relative to healthy controls (Staud et al., 2008; Potvin & Marchand, 2016; Kosek & Ordeberg, 2000).

Therefore, constructing a mechanism-based management strategy of chronic pain requires to find techniques which target the brain processing of nociceptive signals and the central nervous dysfunctions present at chronic pain patients (Macfarlane et al., 2017).

In this vein, non-invasive brain stimulation (NIBS) techniques have become the forefront of novel experimental treatments of chronic pain. Those techniques have proved to be capable of modulating brain activity without surgical interventions and offer new methods to modulate pain-related brain activity in order to reduce pain suffering (Zortea et al., 2019), thus becoming an interesting alternative to traditional therapeutic approaches.

One of these techniques for brain stimulation is the **transcranial Electrical Stimulation (tES)**. By applying a low current over the motor cortex through the scalp, this technique can excite or inhibit the neural activity, thus modulating brain processes like pain perception (Nitsche & Paulus, 2000; Nitsche et al., 2008). The most frequently used tES technique is **transcranial Direct Current Stimulation (tDCS)**. It consists of the application of a constant low-intensity current (1-2 mA) usually through 2 electrodes (anode and cathode) placed on the scalp. This stimulation induces relatively sustained changes in cortical excitability and neuroplasticity (Paulus, 2003). More recently, **transcranial Alternating Current Stimulation (tACS)** has been used to modify cortical functioning (Fröhlich et al., 2015).

Transcranial electrical stimulation may be a key component for correcting defective central pain generating mechanisms. tDCS has been suggested to induce anti-nociceptive effects on experimental pain and have pain-relieving effect in different clinical conditions, using anodal stimulation over the precentral region contralateral to pain (Santos-Portilla et al., 2013). Although different cortical brain targets have been tested, the stimulation of primary motor cortex (M1) appears the most effective cortical target in chronic pain patients and their clinical improvements last beyond the time stimulation, probably due to solid neuroplastic modifications (Lima & Fregni, 2008). This finding is consistent with the hypothesis that cortical networks play a key role in pain processing and that the primary motor cortex (M1) may be a gateway to deep pain-related networks such as the thalamic nuclei and the cingulate gyrus (Baliki et al., 2008; Maarrawi et al., 2007). Evidence for pain reduction through M1 tDCS has been reported for chronic pain manifestations as diverse as pelvic pain, spinal cord pain, cancer, diabetic neuropathy, low-back pain, temporomandibular disorders, and migraine, among others (Lefaucheur, 2016).

Transcranial electric stimulation (tES) has several advantages: it is portable, non-invasive, engineered from low-cost components, has minimal adverse effects, is well

tolerated, easy to use, and multiple animal and clinical studies confirm its safety at low intensities. Recently, a compendium of experts on tDCS released a review covering more than 18,000 stimulation sessions ($\approx 8,000$ patients) in which no significant adverse events were reported for multiple populations (Antal et al., 2017).

Nevertheless, there are some gaps in this field. First, the evidence of its efficacy for pain relief is still limited, as recent Cochrane reviews on the effectiveness of tDCS in chronic pain concluded that the evidence available is not solid enough (O'Connell et al., 2014; 2018). Most current studies still have significant biases (not blinded or placebo-controlled), poor methodological quality (insufficient number of sessions, no follow-ups) and small sample sizes.

Second, previous studies have exclusively focused in tDCS, without paying attention to tACS. In the unique previous clinical trial with chronic low back pain patients, Ahn et al. (2019) found significant correlation between alpha power and pain. Interestingly, stimulation with tACS significantly enhanced alpha oscillations in the somatosensory region, and this increase was correlated with pain relief. Therefore, tACS demonstrate having the potential to relief pain, but it also can help to clarify the mechanism by which tES can modify cortical networks involved in pain (Woods et al., 2016; Peng & Tang, 2016).

Furthermore, no alternatives to the hospital delivery of this treatment have been explored. Although the tES equipment can be controlled remotely and thus allows home-based interventions. At-home interventions are positively perceived by the patients, as they reduce the time involved in treatment and visits to medical centres, favouring self-management of the disease and reducing the burden on family members; also, they increase the efficiency of the professionals, who can attend several patients at the same time.

As we stated before, we are particularly interested in delving into the pathophysiological mechanisms which are associated with chronic pain. Therefore, this clinical trial aims to evaluate the changes in these mechanisms due to the treatment with transcranial electrical stimulation. To this end, we will use two quantitative sensory tests (QST) to assess central nervous dysfunctions in processing and inhibition of pain in clinical population, namely Conditioned Pain modulation (CPM) and Temporal Summation of Second Pain (TSSP).

Conditioned Pain Modulation consists of the reduction of the pain provoked by a given noxious stimulus (i.e., test stimulus) when another painful stimulus (i.e., conditioning stimulus) is applied to a remote area (i.e., pain inhibits pain; Yarnitsky et al., 2010; Willer et al., 1984); whereas TSSP occurs when repeated noxious stimuli over the same corporal area amplifies pain sensations, probably due to a central sensitization derived from the enhanced response of dorsal horn neurons to repetitive nociceptive signals from C-fibers (Dickenson, 1997). Concerning CPM response, approximately 70% of chronic pain patients display a large and statistically significant reduction in their pain inhibition system relative to healthy controls, as evidenced in a meta-analysis by Lewis et al (2012). At the same time, various studies have found greater TSSP in chronic pain patients relative to healthy controls (Staud et al., 2001; Arendt-Nielsen et al., 2010; Petersen et al., 2015)

Altogether, the existing evidence supports that both CPM and TSSP could act as biomarkers of endogenous pain modulation to distinguish chronic pain patients. In fact, the efficiency of these endogenous modulatory pain systems could serve as a predictor of treatment outcomes with tES.

Lastly, the study of brain electrical activity recordings (EEG) in resting state and in response to noxious stimuli may also help to characterize the brain processing of nociceptive stimuli and how these signals are amplified or mitigated (González-Villar et al., 2019). For this reason, another purpose of this research is to evaluate the changes in neural patterns which occurred in chronic pain patients after transcranial electrical stimulation treatment. Specifically, we purport to make a time-frequency and connectivity analysis of the EEG paying special attention to those key frequency bands involved in nociceptive perception (Hu et al., 2013; Liberati et al., 2017; Fallon et al., 2018), namely Theta ($\approx 4-7$ Hz), Alpha ($\approx 8-12$ Hz) and Gamma ($\approx 35-70$ Hz). Brain activity will be recorded both in resting-state (Fallon et al., 2016; Choe et al., 2018) and in response to painful heat and cold stimulation (De Keyser et al., 2018; De Tomasso et al., 2014, 2017).

2. Objectives and hypothesis

The main objective of this clinical trial is to test the efficacy of two different transcranial electrical stimulation techniques (tES) to modify dysfunction of central modulatory mechanisms of pain, and to improve symptoms and quality of life in refractory chronic pain patients.

In this vein, we hypothesize that transcranial electrical stimulation procedures will be more effective than sham to improve pain and related symptoms. Besides, central biomarkers of pain processing and modulation (i.e., CPM, TSSP and EEG) will be useful to predict the patient response to treatment and thus, the efficacy of these tES procedures.

Based in these principal ideas, we propose the following secondary or specific objectives:

- A. To analyse the relationship between the studied biomarkers and clinical pain characteristics of patients (intensity, location, frequency, duration, daily interference caused by pain).
- B. To stratify patients and propose profiles based on the selected biomarkers, which may be useful to improve diagnosis and to guide individualized treatment plans.
- C. To develop home-based treatment schemes for patients with refractory chronic pain. We will assess if tES procedures are safe, feasible and acceptable for the at-home management of this medical condition.
- D. To test if tES techniques are self-manageable by patients and to observe the impact of this treatment in the caregiver-burden declared by the reference person.
- E. To test the efficacy of tDCS (Direct current) versus tACS (Alternant current) to modify dysfunction of central endogenous analgesia (i.e., CPM and TSSP) and to reduce pain and related symptoms in the patients, in a placebo-controlled clinical trial.
- F. To analyze how the different tES techniques (tDCS and tACS) affect brain oscillatory activity, and to test if the changes in oscillatory activity are related to pain relief.
- G. To test the power of the biomarkers/patients' stratification to predict treatment efficacy and to identify the characteristic of best responders patients.

- H. To assess the effect of sex/gender and other modulator variables (age, disease duration, medication, lifestyle, mood...) on all the analyses (central biomarkers, patients' stratification, response to treatment...).

3. Study design

The research is classified as a double-blinded, randomized clinical trial with one control group which receive a sham stimulation.

The transcranial electrical stimulation intervention is considered the independent variable, which contains three different conditions or categories differentiated by the type of stimulation used. These conditions define the three groups of treatment:

- 1) Transcranial direct current stimulation (tDCS), which induces a continuous current over the left primary motor cortex (M1). Current intensity is set at 2mA and it is applied for 20 minutes, with ramp-up and ramp-down of 15 seconds at the beginning and end of the stimulation period.
- 2) Transcranial alternat current stimulation (tACS), which induces an alternant current over somatosensory cortical region. Current intensity is set at 10-Hz and it is applied for 20 minutes, with ramp-up and ramp-down of 15 seconds at the beginning and end of the stimulation period.
- 3) Sham stimulation, which acts as a placebo-control group. It uses the same montage as the previous ones, but it does not emit any kind of current. The position of electrodes will be similar to the previous conditions, but the current will be just activated during the ramp-up and ramp-down moments.

Chronic pain patients are randomly assigned to one of these groups, although the active stimulation conditions agglutinate the 80% of sample (40% tDCS; 40% tACS), whereas the control group contains by the remaining 20%.

As dependent variables, we consider the assessed clinical symptoms, mainly pain characteristics (including intensity, location, frequency, duration and daily interference caused by pain), fatigue, depression/anxiety, sleep quality, physical functioning and life quality, following the guidelines proposed by the *Initiative on Methods, Measurement, and Pain Assessment in Clinical Trials* (IMMPACT; Dworkin et al., 2005).

Besides, as far as we aim to assess the efficacy of tES techniques to restore the potential dysfunctions in processing and modulation of pain in patients, central biomarkers as Conditioned Pain Modulation (CPM), Temporal Summation of Second Pain (TSSP) and EEG are also included as dependant variables. Thus, we try to identify any change in these variables which could be attributable to the intervention.

The intervention and evaluation protocols are more in-depth defined in the following sections.

4. Sample and recruitment

For planning the sample size for this research, we used Gpower (v.3.1.9.2) software. Sample size was estimated for repeated measures ANOVA with three groups (tDCS, tACS, Sham) and two measurements (pre-treatment vs. post-treatment). Statistical power (SP) was predetermined a priori with a value of SP=0.99 ($\alpha=0,01$) to increase the validity of the subsequent analysis and ensure that we do not miss any statistically significant result.

We based the calculation on the data extracted from the meta-analysis by Zortea et al. (2019), who reported a moderate effect size for reduction of pain levels ($F=0.68$) in chronic non-cancer pain patients using the tDCS montage stimulating M1. These results were obtained after comparing 380 patients receiving active tDCS versus 381 who were given Sham stimulation.

Assuming this moderate effect size and the rest of described parameters (SP=0,99), a total of 21 patients would be large enough to detect statistically significant changes in the whole sample. However, it cannot be ignored the non-despicable drop-out rates of this patient profile, corroborated by the own researchers in previous investigations. Besides, we are interested in assessing the effect size of the tDCS intervention among the different categories or types of chronic pain, just as defined by the ICD-11 (Treede et al., 2015), and that requires to create big enough comparable groups. For these reasons, we decided to recruit a larger number of participants, thus stablishing the sample size in 120 patients with refractory chronic pain.

Concerning this research, pain is defined as refractory, regardless of etiology, when it meets the two following conditions. First, multiple evidence-based biomedical therapies

used in a clinically appropriate and acceptable fashion have failed to reach treatment goals that may include adequate pain reduction and/or improvement in daily functioning or have resulted in intolerable adverse effects. Second, pain persists even after psychiatric disorders and psychosocial factors that could be influencing treatment outcomes have been assessed and appropriately addressed.

Epidemiological studies have consistently reported higher prevalence rates of chronic pain syndromes among women, compared to men (Jiménez-Trujillo et al., 2019; Cimas et al., 2018). As we intend to create a feasible and useful tool for clinical practice, these gender differences must also be considered when designing the recruitment plan and deciding the sex distribution of the sample. As we aim to assess the influence of sex/gender in tDCS treatment efficacy and central pain modulation mechanisms, we will recruit both male and female patients, although the latter will represent about 70% of the total sample, in accordance with clinical reality; whereas males will represent at least the 30% of the selected patients, in order to improve and facilitate subsequent comparative analysis. The **inclusion criteria** applied for the selection of patients are the following:

- Suffering a chronic pain condition of non-cancer nature. Those patients who report chronic pain even after overcoming an oncological process are suitable to participate, but only if they have received the definitive medical discharge and have been free from radiotherapy/chemotherapy for at least twelve months.
- Adult subjects (18-65 years old).
- Subjects able to provide informed consent to participate in the study and to self-report pain.
- Existing chronic pain which reaches an intensity of at least 4 on a 0-10 Numeric Rating Scale (NRS) on average over the past 3 months prior to enrolment.
- Pain intensity of at least 5 on a 0-10 NRS over the week prior to enrolment.
- Diagnosis of pharmaco-resistance to analgesic drugs across the WHO ladder.

Participants are allowed to continue with their usual pharmacological regimen, but it must have been stable during the two months previous to the enrolment, and it must not suffer modifications during the whole research period. We will account for the potential effects of some drugs over the efficacy of tDCS/tACS treatment (McLaren et al., 2017), making a registry of patients pharmacological prescriptions to consider them in further

analysis. Rejecting patients who consume medicaments which can apparently interfere with tDCS/tACS effects would not be a well-balanced alternative and would result in a huge loss of participants, since some of these drugs are included as priority treatment for many chronic pain conditions. As far as the **exclusion criteria** are concerned, they are exposed below:

- Chronic pain derived from current cancer disease.
- Pregnant women or women in fertile age not having efficacious contraception during the whole period of the study.
- History of alcohol or drug abuse within the past 6 months as self-reported.
- Suffering from unstable medical conditions (e.g., uncontrolled diabetes, uncompensated cardiac issues, heart failure or chronic obstructive pulmonary disease).
- Intracranial ferromagnetic devices or implanted stimulator (pacemaker, basal ganglia stimulator, vagus nerve stimulation).
- Antecedents of, or active epilepsy.
- History of neurosurgery, psychiatric diseases other than anxiety or depression, traumatic brain injury with loss of consciousness, and/or cortical lesions.

For recruitment phase, we count on the collaboration of three physicians from the Public Health System who work in regional specialized units for the treatment of pain. They will inform those patients who match the inclusion criteria about the existence and nature of the research, offering them the possibility of participating in. Patients who show interest are required to sign an initial consent which allows principal researchers to get in touch with them by telephone. At that moment, patients will be given a more in-depth explanation about the clinical intervention and their implications; researchers will also check that the patient comply with inclusion criteria and he/she does not meet any exclusion criteria.

Those patients who agree to receive the treatment are summoned to a face-to-face session at the research group laboratory. At this stage, patients must sign the informed consent to participate in the research and right after the pre-evaluation protocol is implemented.

In another vein, this research also seeks to determine whether the home-based treatment approach is feasible to be applied by patients themselves and how it affects to the caregiving workload for the reference person¹. To this end, in the initial phone call patients will be asked for identifying that caregiver figure in their own life, in case it effectively exists. Caregiver is defined as the person who worries about the patient's health condition, helps them in daily chores and, in sum, is in charge of covering their emotional and material needs (Bookman & Harrington, 2007).

Identified caregivers are invited to a brief face-to-face interview to evaluate their burden and health status. Given the exploratory character of this purpose, we do not set a priori sample size for caregivers, although the question about the caregiver will be formulated to all the patients.

5. Description of the treatment

Home-based transcranial electrical stimulation device consists of a custom headgear with fixed electrode sites and built-in cabling made for a simplistic setup for tDCS/tACS stimulation. Systems are equipped with strict dose control feature that provide reliable control over the intensity and timing of stimulation, turning these devices into a feasible and safe clinical alternative.

The equipment is specifically designed for easy and simplistic self-setup and allows the researchers to remotely check the position of electrodes and also monitor the stimulation session. This is possible because the devices have an Internet wireless connection and send the data obtained to an online platform, only accessible to the principal researchers.

From pre-stimulation set-up, to during stimulation monitoring, to post-stimulation confirmation, the device provides an intuitive and clear indication of electrode contact quality, facilitating the proper adjustments to ensure a successful stimulation. In case stimulation is aborted or interrupted, impedance is abnormal, or other faults are detected, the system will automatically abort or alter stimulation and the incident details stored. This system also allows researchers to supervise the treatment compliance.

¹ It must not be overlooked that patients with chronic pain can find difficulties/limitations to accomplish the basic daily tasks and thereby be partially dependant (Meulders, 2019; Zale et al., 2013)

Besides, these devices use a software which allows a double-blinded procedure. Neither the researchers nor the participants will know what kind of stimulation is receiving each of them.

The intervention plan comprises fifteen stimulation sessions applied with a daily frequency during an uninterrupted period of time which covers just over two weeks. Thus, sessions will be scheduled for each patient before the beginning of the treatment, arranging with the patient the hour frame for stimulation. Stimulation parameters/sites for each condition will be as follows:

- Transcranial direct current stimulation (tDCS). Current intensity of 2mA applied during 20 minutes at the left M1, with anodal electrode placed in C3 and cathodal in FP2, following the International 10-20 EEG System. Ramp-up and ramp-down comprises 15 seconds at the beginning and end of the stimulation period.
- Transcranial alternating current stimulation (tACS). Following the design established by previous studies (Ahn et al., 2019), two electrodes will be placed at F3 and F4 and connected together for 10-Hz tACS (or the frequency which shows best sensitivity or specific), and one electrode at Pz will be the return electrode. This setting is used to stimulate the somatosensory cortical region. Stimulation will last for 20 minutes, with a ramp-up and ramp-down of 15 seconds at the beginning and end of the session.
- Sham stimulation. The electrode montage will be either the tDCS (for half of the participants) or the tACS montage (for the other half), and we will just apply the current at the ramps terms, but no current in the interval between the ramps which practically comprises the whole session.

At the second pre-treatment evaluation session, patients will receive the portable stimulator with the proper explanations about its functioning. It is planned to make a training stimulation session during this visit to ensure that patients are able to connect and manage the device.

6. Evaluation protocol and follow-up

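### The claim that 21 patients give 0.99 power rests on a between-arm difference of about 2.8 to 2.9 SD of the change score, not a moderate effect, and no power is given for the 120 planned

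*Combined protocol and SAP*

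**What the plan says.** Section 4 describes a G*Power calculation for a repeated measures ANOVA with three groups and two measurements. It says "Statistical power (SP) was predetermined a priori with a value of SP=0.99", at alpha 0.01, with the aim to "ensure that we do not miss any statistically significant result". The effect size comes from a meta-analysis that "reported a moderate effect size for reduction of pain levels ($F=0.68"), a figure obtained by "comparing 380 patients receiving active tDCS versus 381 who were given Sham stimulation". From this the section concludes that "a total of 21 patients would be large enough to detect statistically significant changes in the whole sample". Citing drop-out and an interest in pain-type groups, it continues: "we decided to recruit a larger number of participants, thus stablishing the sample size in 120 patients".

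The section does not state whether 0.68 is Cohen's f or a standardized mean difference, whether the effect tested is time or group-by-time, what pre-post correlation was used, what drop-out rate is expected, or what power 120 patients give.

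Three other places bear on this:
- Section 2 (Objectives and hypothesis): "we hypothesize that transcranial electrical stimulation procedures will be more effective than sham to improve pain and related symptoms".
- Section 3 (Study design): "the active stimulation conditions agglutinate the 80% of sample (40% tDCS; 40% tACS), whereas the control group contains by the remaining 20" percent.
- Section 7 (Data analysis plan): the main efficacy analysis is a pre-post repeated measures ANOVA across the three stimulation groups. No significance level is given there.

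**The concern.** Twenty-one patients in three arms is about seven per arm. Power of 0.99 at alpha 0.01 from so few patients can only come from a very large separation between arms, yet the effect is described as moderate and comes from a two-group comparison. The calculation also ignores the unequal allocation fixed in section 3.

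This paragraph is the trial's only sample-size justification. It presents 120 as a margin over 21 large enough to absorb drop-out and support comparisons by pain type. If the 21 does not describe the active-versus-sham question at a realistic effect, the size of that margin is unknown, and a reader cannot tell what difference the trial can detect with 24 sham patients.

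**Working it through.** **Inputs from the documents.** Three groups (k=3), two measurements (m=2), alpha 0.01, power 0.99, effect size 0.68, N=21 calculated, N=120 planned, allocation 40/40/20 (8.4/8.4/4.2 of 21; 48/48/24 of 120).

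**Assumptions, not in the documents.** Pre-post correlation ρ, drop-out rate, and the pattern of effects across arms. Unless stated otherwise, both active arms differ from sham by the same amount d.

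**1. Reproducing 21.** G*Power form of the interaction test: λ = f²·N·m/(1−ρ), with 2 and N−3 degrees of freedom. With f=0.68 and ρ=0.5:
- N=18: λ = 0.4624 × 18 × 2 / 0.5 = 33.29, power 0.976.
- N=21: λ = 0.4624 × 21 × 2 / 0.5 = 38.84, power 0.994.

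So 21 is the first multiple of three to reach 0.99. It is not the only route to 21:
- Time (within) effect, f=0.68, 1 and N−3 degrees of freedom: 21 results for ρ of about 0.35 to 0.45.
- Interaction with f=0.34 (0.68 halved, as for a two-group d): 21 results for ρ of about 0.87 to 0.89.

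**2. What 21 implies for the interaction, whatever was entered.** With two measurements the interaction is a one-way F test on change scores. With d in SDs of the change score, λ = d²·n_sham·(N − n_sham)/N. At 7/7/7 this is d² × 7 × 14/21 = 4.667d². Power 0.99 on 2 and 18 degrees of freedom at alpha 0.01 needs λ = 36.23, so d = √(36.23/4.667) = 2.79. This does not depend on f or ρ. It is also the smallest possible largest gap between arms: a graded pattern (d, d/2, 0) needs 3.22.

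For f=0.68 and ρ=0.5, λ = 38.84 gives d = √(38.84/4.667) = 2.885, about 2.9 SD.

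**3. The plan's own allocation.** At 8.4/8.4/4.2, λ = d² × 4.2 × 16.8/21 = 3.36d².

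| Difference and pattern | 7/7/7 | 40/40/20 |
|---|---|---|
| 2.885 SD, both active arms equal | 0.994 | 0.956 |
| 2.79 SD, both active arms equal | 0.990 | 0.940 |
| 2.885 SD, only one active arm differs | 0.994 | 0.997 |

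In whole patients, 2.885 SD with equal active arms gives 0.948 at 9/8/4 and 0.977 at 8/8/5. To keep 0.99 at 40/40/20 with equal active arms, d must be √(36.23/3.36) = 3.28.

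**4. If 0.68 is a difference in SDs of the change score.** At 7/7/7, λ = 4.667 × 0.68² = 2.16, and 21 patients have power 0.07.

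**5. The 120 planned.** At 48/48/24, λ = d² × 24 × 96/120 = 19.2d², with 2 and 117 degrees of freedom.
- 0.68 as f: power above 0.999 at alpha 0.01 with ρ=0.5.
- 0.68 as a d converted to f=0.34: 0.990 at ρ=0.3 and 0.999 at ρ=0.5, alpha 0.01.
- 0.68 as an active-sham difference in change, in single-time SDs: d = 0.68/√(2(1−ρ)), as below.

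| ρ | d (change-score SD) | Power, alpha 0.01 | Power, alpha 0.05 |
|---|---|---|---|
| 0.3 | 0.575 | 0.35 | 0.60 |
| 0.5 | 0.680 | 0.52 | 0.75 |
| 0.7 | 0.878 | 0.81 | 0.94 |
| 0.8 | 1.075 | 0.96 | 0.99 |

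**6. A statement that does not depend on the metric.** At 48/48/24, 80% power needs d = 0.87 at alpha 0.01 and 0.72 at 0.05. With an assumed 20% drop-out (38/38/19, so λ = 15.2d²), it needs 0.98 and 0.81.

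**The case against.** The strongest reply is that 21 is correct arithmetic. The symbol F suggests Cohen's f, and with that reading, a correlation of 0.5 and equal arms, the plan's number comes out. Nobody will run 21 patients, and on that reading 120 is ample. This stands as far as it goes: the fault lies in the effect size and the 0.99 claim built on it, not in the calculation.

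The plan's phrase about changes in the whole sample also fits a test of time, which needs no between-arm difference at all, so the 2.79 SD figure applies only if the interaction was tested. That stands too, but it does not rescue the claim. A time effect would appear if every arm, sham included, improved alike, so it does not test whether stimulation beats sham.

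The drop to 0.956 depends on equal active effects, which the plan does not assume; objective E compares tDCS with tACS. It is a conditional figure and should be quoted as one.

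A reader might go further and infer that the authors entered a d as an f, or that the trial is underpowered at 120. The documents support neither. The source figure cannot be checked from them, and low power at 120 arises only on one reading of 0.68. The low end also needs a correlation near 0.3, which is less natural for fifteen-day averages of daily ratings, though no value is given.

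**Conclusion.** The concern holds in a limited form. For the group-by-time interaction, which is the test that addresses the trial's hypothesis, 0.99 power with 21 patients in equal arms requires arms at least 2.79 SD of the change score apart. That bound rests on no assumed correlation or f, and it cannot be squared with an effect called moderate. If a time effect was used instead, the calculation does not address the hypothesis. Either way the 21-patient, 0.99-power statement does not justify the sample size.

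Whether 120 is a real surplus is open: about 0.99 or more on two readings of 0.68, and 0.35 to 0.96 at alpha 0.01 on the third, for assumed correlations of 0.3 to 0.8 and equal active effects. Confidence is high about the 21-patient statement. There is no basis in the documents for choosing between the readings of 0.68.

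**What to change.** Replace the 21-patient justification in section 4 with power for the design that will be run. Name the group-by-time interaction, and the stimulation-versus-sham contrast, as the effects tested, and state the metric of 0.68 and how it was converted. Give the analysis alpha and the assumed drop-out rate. Wording that does not depend on the metric:

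*With 120 patients allocated 48/48/24, the three-group test of change has 80% power for a difference of both active arms from sham of 0.87 SD of the change score at alpha 0.01 (0.72 at 0.05); with an assumed 20% drop-out, 0.98 and 0.81.*

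If the 21 is kept, state that 0.68 is Cohen's f, drop the word moderate, and give the implied difference (about 2.9 SD) and the power at 40/40/20 with the assumed pattern of effects.

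The cost is one reworded paragraph, with no added patients or visits and no design change. The stated power may become less favourable.
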